6.4.3 Guidelines for Dose Modification: Specific Hematologic Toxicities

Consider use of granulocyte colony-stimulating factor (G-CSF) as per institutional guidelines or as per American Society of Clinical Oncology (ASCO) guidelines for neutropenia/febrile neutropenia.

For anemia, consider use of erythropoietin as per institutional guidelines.

If a patient experiences hematologic toxicity of \geq Grade 3 neutropenia or thrombocytopenia, camidanlumab tesirine must be held until the toxicity resolves to \leq Grade 2.

6.4.4 Guidelines for Dose Modification: Specific Neurologic Toxicities

Patients experiencing any new neurological toxicities and/or new onset of pain refractory to common pain medications ≥ Grade 1, not explained by previous medical history, that could be linked to or may be an early indicator of polyradiculopathy/GBS, such as ascending (bilateral) sensory loss or motor weakness, need to be immediately evaluated by a neurologist and dosing of camidanlumab tesirine must be held until polyradiculopathy/GBS is ruled out. Please refer to Section 6.7.5 for management of polyradiculopathy/GBS, especially for the recommendation of prompt initiation of therapy upon reasonable suspicion of polyradiculopathy/GBS. Should further clinical, radiologic, or laboratory evidence support the diagnosis of polyradiculopathy/GBS with Level 1 diagnostic certainty (Section 6.7.5 and Appendix 13.2), treatment with camidanlumab tesirine must be permanently discontinued.

Patients with \geq Grade 3 neurologic toxicities defined as peripheral sensory and peripheral motor neuropathies and not explained by previous medical history must have treatment with camidanlumab tesirine permanently discontinued.

Other new neurological findings not explained by previous medical history with an increase of ≥ 1 Grade over Baseline will result in dose delay; dosing may be resumed after resolution to Baseline, at the Investigator's discretion. The patient must be carefully monitored at least weekly until such resolution (can be done by telephone unless symptoms worsen).

6.4.5 Guidelines for Dose Modification: Specific Skin Toxicities

Adverse Event	Grade	Camidanlumab Tesirine Management Guideline
Maculopapular rash	1	No dose adjustment is required and monitor for change in severity.
or		Topical treatment to affected areas is indicated:
Photosensitivity rash		 maculopapular rash, photosensitivity rash, or pruritus: high potency topical steroid cream (e.g., clobetasol propionate 0.05%, halobetasol propionate 0.05%) xerosis or hyperpigmentation: consider ammonium lactate 12% or urea 20% BID.
or		Reassessment every 2 weeks is indicated (either by healthcare professional or patient self-report).
Pruritus	2	No dose adjustment is required and monitor for change in severity.
or		Topical treatment to affected areas is indicated:
Xerosis		- maculopapular rash or photosensitivity rash: high potency topical steroid cream (e.g., clobetasol propionate 0.05%, halobetasol propionate 0.05%).
or		- pruritus: high potency topical steroid cream and consider oral antipruritic (e.g., hydroxyzine, gabapentin, or pregabalin).
Hyperpigmentation		- xerosis or hyperpigmentation: consider ammonium lactate 12% or urea 20% BID.
		Reassessment every 2 weeks is indicated (either by healthcare professional or patient self-report).
		In case these Grade 2 rashes become intolerable, Grade 3 recommendations may be applied.
	3	Hold camidanlumab tesirine until improvement to ≤ Grade 1 or Baseline and consider dermatology consult.
		Topical treatment to affected areas is indicated and consider systemic corticosteroid treatment e.g., prednisone 0.5 mg/kg for 10 days:
		 maculopapular rash or photosensitivity rash: high potency topical steroid cream (e.g., clobetasol propionate 0.05%, halobetasol propionate 0.05%) and consider prednisone 0.5 mg/kg for 10 days. pruritus: high potency topical steroid cream (e.g., clobetasol propionate 0.05%, halobetasol
		propionate 0.05%) and consider oral antipruritic (e.g., hydroxyzine, gabapentin, or pregabalin). - xerosis or hyperpigmentation: consider ammonium lactate 12% or urea 20% BID; and triamcinolone 0.1% cream BID.

Adverse Event	Grade	Camidanlumab Tesirine Management Guideline
		Reassessment every 2 weeks is indicated (either by healthcare professional or patient self-report); if reactions do not improve, then:
		First Occurrence:
		• If improvement to ≤ Grade 1 or Baseline occurs prior to the next scheduled dose, proceed with the originally planned camidanlumab tesirine dose level.
		• If improvement to ≤ Grade 1 or Baseline occurs > 21 days from the last scheduled (but missed) camidanlumab tesirine dose, reduce from 45 to 30 μg/kg or from 30 to 20 μg/kg.
		Second Occurrence:
		• If improvement to ≤ Grade 1 or Baseline occurs, reduce from 45 to 30 μg/kg or from 30 to 20 μg/kg.
		Third Occurrence:
		Permanently discontinue camidanlumab tesirine.
	4	Hold camidanlumab tesirine until improvement to ≤ Grade 1 or Baseline and consider dermatology consult.
		Topical treatment to affected areas is indicated and consider systemic corticosteroid treatment, e.g., prednisone 0.5 mg/kg for 10 days:
		- maculopapular rash or photosensitivity rash: high potency topical steroid cream (e.g., clobetasol propionate 0.05%, halobetasol propionate 0.05%) and consider prednisone 0.5 mg/kg for 10 days.
		 pruritus: high potency topical steroid cream (e.g., clobetasol propionate 0.05%, halobetasol propionate 0.05%) and consider oral antipruritic (e.g., hydroxyzine, gabapentin, or pregabalin). xerosis or hyperpigmentation: consider ammonium lactate 12% or urea 20% BID; and triamcinolone 0.1% cream BID.
		Reassessment every 2 weeks is indicated (either by healthcare professional or patient self-report); if reactions do not improve, then:
		First Occurrence:
		• If improvement to ≤ Grade 1 or Baseline occurs, continue camidanlumab tesirine and reduce from 45 to 30 μg/kg or from 30 to 20 μg/kg.
		Second Occurrence:
		Permanently discontinue camidanlumab tesirine.

Adverse Event	Grade	Camidanlumab Tesirine Management Guideline
Blistering rash	1	No dose adjustment is required and monitor for change in severity. Consider dermatology consult
		Topical treatment to affected areas is indicated, e.g., silvadene 1% cream BID and consider laboratory testing for blistering disorder (VZV/HSV and bacterial infection; bullous pemphigoid; pemphigus).
		Reassessment every 2 weeks is indicated (either by healthcare professional or patient self-report).
	2/3	Hold camidanlumab tesirine until improvement to ≤ Grade 1 or Baseline and consider dermatology and wound care consult.
		Topical treatment to affected areas is indicated, e.g., silvadene 1% cream BID, and consider laboratory testing for blistering disorder (VZV/HSV and bacterial infection; bullous pemphigoid; pemphigus) and consider systemic corticosteroid treatment, e.g., prednisone 0.5 mg/kg for 10 days.
		Reassessment every 2 weeks is indicated (either by healthcare professional or patient self-report); if reactions do not improve, then:
		First Occurrence:
		 If improvement to ≤ Grade 1 or Baseline occurs prior to the next scheduled dose, proceed with the originally planned camidanlumab tesirine dose level.
		 If improvement to ≤ Grade 1 or Baseline occurs > 21 days from the last scheduled (but missed) camidanlumab tesirine dose, continue camidanlumab tesirine and reduce from 45 to 30 µg/kg or from 30 to 20 µg/kg.
		Second Occurrence:
		• If improvement to ≤ Grade 1 or Baseline occurs, reduce from 45 to 30 μg/kg or from 30 to 20 μg/kg.
		Third Occurrence:
		Permanently discontinue camidanlumab tesirine.
	4	Hold camidanlumab tesirine until improvement to ≤ Grade 1 or Baseline and consider dermatology consult.
		Topical treatment to affected areas is indicated, e.g., silvadene 1% cream BID, and consider laboratory testing for blistering disorder (VZV/HSV and bacterial infection; bullous pemphigoid; pemphigus) and consider systemic corticosteroid treatment, e.g., prednisone 0.5 mg/kg for 10 days.
		Reassessment every 2 weeks is indicated (either by healthcare professional or patient self-report); if reactions do not improve, then:
		First Occurrence:
		• If improvement to ≤ Grade 1 or Baseline occurs, continue camidanlumab tesirine and reduce from 45 to 30 μg/kg or from 30 to 20 μg/kg.

Adverse Event	Grade	Camidanlumab Tesirine Management Guideline	
		Second Occurrence:	
		Permanently discontinue camidanlumab tesirine.	

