6.3 Camidanlumab Tesirine Dosing

Camidanlumab tesirine will be administered at a dose of 45 μ g/kg Q3W for 2 cycles, then 30 μ g/kg for subsequent cycles.

Refer to Section 6.7 for premedication and supportive care.

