6.4 Dose Delays and Modifications

The Investigator may suspend camidanlumab tesirine dosing for up to 21 days, for any patient who experiences any toxicity of any grade.

Resumption of dosing with camidanlumab tesirine after any suspension, even when longer than 21 days, is at the discretion of the Investigator, on assessment of the patient's clinical condition and whether or not the patient is deriving potential clinical benefit from treatment with camidanlumab tesirine.

The Investigator may also suspend camidanlumab tesirine dosing for any patient scheduled for HSCT in the near future, and resumption of dosing is only allowed if the patient has not received in the meantime any chemotherapy-based mobilization/conditioning therapy or HSCT.

Management of toxicities, when considered to be at least possibly related to camidanlumab tesirine, must be performed according to:

- Section 6.4.1 for general events (i.e., not specified in the below sections),
- Section 6.4.2 for specific non-hematologic events,
- Section 6.4.3 for specific hematologic events,
- Section 6.4.4 for specific neurologic events,

• Section 6.4.5 for specific skin events.

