6.4.1 Guidelines for Dose Modification: General

AE Grade	Camidanlumab Tesirine Management Guideline			
1/2	No dose adjustment is required.			
3/4	First Occurrence:			
	 Hold camidanlumab tesirine until improvement to ≤ Grade 1 or Baseline. 			
	• If improvement to ≤ Grade 1 or Baseline occurs prior to the next scheduled dose, proceed with the originally planned camidanlumab tesirine dose level.			
	• If improvement to ≤ Grade 1 or Baseline occurs > 21 days from the last scheduled (but missed) camidanlumab tesirine dose, continue camidanlumab tesirine and reduce from 45 to 30 μg/kg or from 30 to 20 μg/kg.			
	Second Occurrence:			
	• Hold camidanlumab tesirine until improvement to ≤ Grade 1 or Baseline, reduce from 45 to 30 μg/kg or from 30 to 20 μg/kg.			
	Third Occurrence:			
	Permanently discontinue camidanlumab tesirine.			

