6.4.2 Guidelines for Dose Modification: Specific Non-hematologic Toxicities

Adverse Event	Grade	Camidanlumab Tesirine Management Guideline
Infusion-related reactions	1	The infusion rate may be decreased or temporarily interrupted to permit resolution of the event. If the total time for dilution into the IV bag and infusion takes longer than 4 hours, the remaining solution of camidanlumab tesirine will be discarded and the dosing will continue with the assigned dose at the next scheduled dosing visit. Please refer to Section 6.7.3 for treatment recommendation.
	2	Interrupt camidanlumab tesirine infusion to permit resolution of the event. If the event resolves within the total time of 4 hours after dilution into the IV bag and infusion time, resume camidanlumab tesirine infusion at 50% of the prior infusion rate, still not exceeding the total of 4 hours after infusion has restarted.
		If the resolution takes longer than the total 4 hours, the remaining solution of camidanlumab tesirine will be discarded, and the dosing will continue with the assigned dose at the next scheduled dosing visit at 50% of the prior infusion rate. Please refer to Section 6.7.3 for treatment recommendation.
	3	Permanently discontinue camidanlumab tesirine. However, if the AE resolves within 24 hours after onset (with or without clinical management), dosing may continue with the assigned dose at the next scheduled dosing visit at 50% of the prior infusion rate.
		Please refer to Section 6.7.3 for treatment recommendation.
	4	Permanently discontinue camidanlumab tesirine.
AST, ALT, or GGT abnormalities	2/3	 First Occurrence: Hold camidanlumab tesirine until improvement to ≤ Grade 1 or Baseline. If improvement to ≤ Grade 1 or Baseline occurs prior to
Edema		the next scheduled dose, proceed with the originally planned camidanlumab tesirine dose level.
or Effusion		 If improvement to ≤ Grade 1 or Baseline occurs > 21 days from the last scheduled (but missed) camidanlumab tesirine dose, reduce from 45 to 30 μg/kg or from 30 to 20 μg/kg.
		Second Occurrence:
		 Hold camidanlumab tesirine until improvement to ≤ Grade 1 or Baseline.
		• If improvement to ≤ Grade 1 or Baseline occurs, reduce from 45 to 30 μg/kg or from 30 to 20 μg/kg.

Adverse Event	Grade	Camidanlumab Tesirine Management Guideline	
		Third Occurrence:	
		Permanently discontinue camidanlumab tesirine.	
	4	First Occurrence:	
		 Hold camidanlumab tesirine until improvement to ≤ Grade 1 or Baseline. 	

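### Protocol 6.4.5 places its skin-toxicity dosing ladders under a condition of non-improvement, so read literally no reduction or stop rule binds a patient who improves

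*Protocol*

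**What the plan says.** Section 6.4 of the protocol makes the dose-modification tables binding for toxicities judged at least possibly drug-related: management of such events, in relation "to camidanlumab tesirine, must be performed according to" the listed subsections. Skin events fall under 6.4.5. The general table is a residual category only: "Section 6.4.1 for general events (i.e., not specified in the below sections").

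In 6.4.5, four blocks hold study drug: the non-blistering group (maculopapular or photosensitivity rash, pruritus, xerosis, hyperpigmentation) at Grade 3 and at Grade 4, and blistering rash at Grade 2/3 and at Grade 4. Each has three parts in the same order.

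- A hold, for example in both non-blistering blocks: "Hold camidanlumab tesirine until improvement to ≤ Grade 1 or Baseline and consider dermatology consult". It ends on recovery and names no restart dose.
- Supportive treatment, closing with "Reassessment every 2 weeks is indicated (either by healthcare professional or patient self-report); if reactions do not improve, then".
- A ladder by first, second and (where present) third occurrence. Every resume or reduce rule in it starts from recovery to Grade 1 or lower, or to baseline. The late-recovery rule in the non-blistering Grade 3 block, for instance, applies when recovery "occurs > 21 days from the last scheduled (but missed) camidanlumab tesirine dose, reduce from 45 to 30" μg/kg, or from 30 to 20. The last step of each ladder is a permanent stop with no recovery condition of its own.

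The lower-grade rows that do not hold drug contain the same reassessment sentence without the conditional ending.

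The comparable ladders have no such lead-in. In 6.4.1 the second-occurrence rule is "Hold camidanlumab tesirine until improvement to ≤ Grade 1 or Baseline, reduce from 45 to 30" (or 30 to 20); in 6.4.2 it is "If improvement to ≤ Grade 1 or Baseline occurs, reduce from 45 to 30" (or 30 to 20).

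**The concern.** The lead-in admits a patient to the ladder only if the reaction has not improved, while the resume and reduce rules below it act only once it has. A site that takes the sentence at its word has no dosing rule for a patient whose reaction is better at the two-week check.

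The stop rules are the most exposed part. Because they carry no recovery condition, they read quite naturally under the lead-in: a second Grade 4 reaction, or a third at the lower grade, that fails to improve means stop. An investigator could in good faith continue dosing a patient whose second Grade 4 rash resolved. The 6.4.2 ladder for liver enzymes, edema and effusion requires a stop at the second Grade 4 occurrence whether or not it resolves.

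At stake are the dose given after a repeat or Grade 4 skin reaction, the point at which treatment must end, and whether sites apply the same rule.

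**Working it through.** The plan gives no count of these rules, so there is no stated figure to reproduce. The rules under the lead-in, tallied from 6.4.5:

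| Block | Resume at planned dose | Reduce, recovery > 21 days | Reduce, second occurrence | Reduce, first Grade 4 | Permanent stop | Total |
|---|---|---|---|---|---|---|
| Non-blistering Grade 3 | 1 | 1 | 1 | 0 | 1 | 4 |
| Non-blistering Grade 4 | 0 | 0 | 0 | 1 | 1 | 2 |
| Blistering Grade 2/3 | 1 | 1 | 1 | 0 | 1 | 4 |
| Blistering Grade 4 | 0 | 0 | 0 | 1 | 1 | 2 |
| All | 2 | 2 | 2 | 2 | 4 | 12 |

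**Rules at odds with the lead-in.** Those triggered by recovery: 2 + 2 + 2 + 2 = 8 of 12.

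**Literal scope.** The lead-in stands above the whole ladder, so it switches off 12 of 12 rules for a patient who improves at reassessment.

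**Effect on that patient.** Going through the 12:

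- The 2 resume rules return the patient to the planned dose, which is also what happens with no ladder. Nothing changes.
- The 2 second-occurrence reductions, 2 first Grade 4 reductions and 4 stops are lost: 2 + 2 + 4 = 8.
- The 2 late-recovery reductions depend on what improvement means. More than 21 days with reassessment every 14 days gives at least floor(21/14) = 1 reassessment before recovery. If improvement means full recovery to Grade 1 or baseline, the patient had not improved at that check and the rule can apply. If partial improvement counts, the rule may be lost as well: 8 + 2 = 10.

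The two eights are different sets. The first holds the resume and reduce rules; the second leaves out the resume and late-recovery rules and adds the four stops.

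**Dose difference.** Section 6.3 plans 45 μ"g/kg Q3W for 2 cycles, then 30" μg/kg.

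- Reaction at the 30 μg/kg dose: 30 given instead of 20, and 30/20 − 1 = 50% more, for as long as dosing continues.
- Reaction after the Cycle 1 dose: 45 instead of 30 at Cycle 2, and 45/30 − 1 = 50%, for that one dose.
- Reaction after the Cycle 2 dose: if reducing from 45 to 30 simply yields the dose already planned for Cycle 3, the difference is 30/30 − 1 = 0. If it means one level below the planned 30, it is 30 against 20 again.

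**What else applies to the improving patient.** The hold, but it sets no restart dose. Mandatory discontinuation for unacceptable toxicity (5.5.1), but without an occurrence count. The Investigator's discretion over resuming (6.4), which is judgement. The general ladder in 6.4.1 does not formally apply, because skin events are specified elsewhere.

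**The case against.** The best defence is that the wording can be followed in sequence. A patient fails to improve at one two-week check, recovers later, and then enters the ladder. On that path the lead-in and the recovery-triggered rules are compatible. That stands: a reader might infer that the table contradicts itself and cannot be applied, and the text does not support that. The fault is ambiguous drafting that leaves out the patient who improves at the first check.

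The second defence is intent. The hold lies outside the lead-in, each rule states its own trigger, and the ladders in 6.4.1 and 6.4.2 are unconditional, so many investigators would apply the skin ladder to every held patient. That is probably what the authors meant. It does not dispose of the point: the conditional ending appears in all four hold blocks and in none of the lower-grade rows, so it looks deliberate, and the stop rules make sense under it.

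A reader might also take the 17% of 77 Phase 1 cHL patients with maculopapular rash of Grade 3 or higher (protocol 1.3) as a ceiling on the number affected. It is not one. Under 6.4.5, intolerable Grade 2 rashes may be managed as Grade 3, blistering rash enters its ladder at Grade 2, and the Phase 1 figure covers a single event at mixed doses (13/77 = 16.9%, exact 95% CI 9.3% to 27.1%).

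Finally, a reader might infer that an unreduced dose is automatically an important deviation under SAP 4.3, since 50% exceeds its 15% limit. That limit is measured against the planned dose level, and the SAP does not say whether a level reduced for toxicity counts as planned.

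**Conclusion.** The point holds as a drafting fault in a mandatory safety-dosing table. Literally, none of the 12 rules binds a patient who improves at reassessment; in effect 8 required reductions or stops are lost, or 10 if partial improvement counts. The dose difference can be 50% (30 versus 20 μg/kg), and may be nil for a reaction after the Cycle 2 dose. The remaining safeguards fix neither a restart dose nor a stopping point by occurrence.

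This rests on reading the lead-in as governing the whole ladder beneath it, which is how the table is laid out. The documents give no rate for repeat or Grade 4 skin reactions, so the number of affected patients can be neither estimated nor bounded.

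It would be wrong to infer a threat to the efficacy result. The primary analyses use all treated patients, the per-protocol ORR is only a sensitivity analysis to be run if relevant (SAP 4.9.1), and the sample size, power and ORR definition do not depend on this table. The change is worth making on safety and consistency grounds alone.

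**What to change.** In all four hold blocks of 6.4.5, delete the conditional ending of the reassessment sentence, or move it to the supportive-care step so that lack of improvement at two weeks prompts escalation of treatment or referral to dermatology. Open the ladder instead with *dose according to occurrence as follows*. It then applies to every held skin reaction, as in 6.4.1 and 6.4.2.

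The cost is a wording change in four rows of one table, with no added visits, tests or data.

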6.5 Overdose Management

An overdose is any dose of study drug given to a patient that exceeds the maximum dose described in the protocol by 15% or more. Any overdose, with or without associated AEs, must be promptly (i.e., within 24 hours after the time site personnel first learn about the event) reported to the Sponsor.

There are no data available to determine what the effects of overdose are and whether they can be reversed. Symptomatic treatment and standard supportive care measures for the management of any observed toxicity should be applied.

If feasible, a sample for PK analysis should be taken as close as possible to the overdose event.

6.6 Treatment Compliance

Administration of the study drug will be performed by the Investigator or a qualified designee; therefore, compliance will be verified by the study drug administration information.

6.7 Premedication and Supportive Care

6.7.1 Premedication

Unless contraindicated, administer dexamethasone 4 mg orally twice daily (BID), or equivalent, the day before camidanlumab tesirine administration (if possible), the day of camidanlumab tesirine administration (give at least 2 hours prior to administration when not given the day before; otherwise any time prior to administration), and the day after camidanlumab tesirine administration.

[**For Italy Sites Only:** Prednisone 25 mg BID is the only equivalent to the dexamethasone 4 mg BID dose permitted as alternative premedication. The dosing schedule of dexamethasone and prednisone is the same.]

Patients who experience an infusion-related hypersensitivity reaction will receive the alternative premedication regimen specified in Section 6.7.3.

6.7.2 Treatment of Edema and Pleural Effusion

Spironolactone at standard doses should be administered for patients with weight gain greater than 1 kg from C1D1, new or worsening edema, and/or new or worsening pleural effusion. The dose of spironolactone may be titrated as clinically indicated. Additional diuretic support may be added if there is further increase in weight, edema, or pleural effusion. Additionally, patients should be advised to monitor their weight on a daily basis, at around the same time (preferably in the morning), and to notify the study site if they gain > 1 kg (2.2 pounds) over Baseline.

